7.0 TRIAL PROCEDURES

7.1 Trial Procedures

The charts in Section 6.0 summarize the trial procedures to be performed at each visit. Individual trial procedures are described in detail below. It may be necessary to perform these procedures at unscheduled time points if deemed clinically necessary by the investigator.

Furthermore, additional evaluations/testing may be deemed necessary by the investigator and/or Merck for reasons related to subject safety. In some cases, such evaluation/testing may be potentially sensitive in nature (e.g., HIV, Hepatitis C, etc.), and thus local regulations may require that additional informed consent be obtained from the subject. In these cases, such evaluations/testing will be performed in accordance with those regulations.

7.1.1 Administrative Procedures

7.1.1.1 Informed Consent

The study team must obtain documented consent from each potential subject prior to participating in a clinical trial.

Consent must be documented by the subject's dated signature. A copy of the signed and dated consent form should be given to the subject before participation in the trial.

The initial informed consent form, any subsequent revised written informed consent form and any written information provided to the subject must receive the Institutional Review Board's (IRB's) approval/favorable opinion in advance of use. The subject should be informed in a timely manner if new information becomes available that may be relevant to the subject's willingness to continue participation in the trial. The communication of this information will be provided and documented via a revised consent form or addendum to the original consent form that captures the subject's dated signature.

7.1.1.2 Inclusion/Exclusion Criteria

All inclusion and exclusion criteria will be reviewed by the investigator or qualified designee to ensure that the subject qualifies for the trial.

7.1.1.3 Medical History

A medical history will be obtained by the investigator or qualified designee. Medical history will include all active conditions, and any condition diagnosed within the prior 10 years that are considered to be clinically significant by the investigator. Details regarding the patients' prior treatment for SCCHN will be recorded separately and not listed as medical history.

7.1.1.4 Prior and Concomitant Medications Review

7.1.1.4.1 Prior Medications

The investigator or qualified designee will review prior medication use, including any protocol-specified washout requirement, and record prior medication taken by the subject within 30 days

before starting the trial. Treatment for the disease for which the subject has enrolled in this study will be recorded separately and not listed as a prior medication.

7.1.1.4.2 Concomitant Medications

The investigator or qualified designee will record medication, if any, taken by the subject during the trial. All medications related to reportable SAEs and ECIs should be recorded as defined in Section 7.2.

7.1.1.5 Disease Details and Treatments

7.1.1.5.1 Disease Details

The investigator or qualified designee will obtain prior and current details regarding the patient's SCCHN, including all prior treatments received.

7.1.1.5.2 Prior Treatment Details

The investigator or qualified designee will review all prior cancer treatments including systemic treatments, radiation and surgeries.

7.1.1.5.3 Subsequent Anti-Cancer Therapy Status

The investigator or qualified designee will review all new anti-neoplastic therapy initiated after the last dose of trial treatment. If a subject initiates a new anti-cancer therapy within 30 days after the last dose of trial treatment, the 30 day Safety Follow-up visit must occur before the first dose of the new therapy. Once new anti-cancer therapy has been initiated, the subject will move into survival follow-up.

7.1.1.6.4 Patient Reported Outcomes

The EORTC QLQ C-30 and EORTC QLQ-H&N35 questionnaires will be administered by site personnel and completed by subjects at time points shown in the flow charts above. The EORTC QLQ C-30 will be completed first, followed by the EORTC QLQ-H&N35.

7.1.1.6 Assignment of Subject Number

All consented subjects will be given a unique number. The performance site should contact the coordinating center to obtain each subject's unique, sequential number. That number will be used to identify the subject throughout the study. The number will not contain any direct subject identifiers.

7.1.1.7 Trial Compliance (Medication/Diet/Activity/Other)

Administration of trial medication will be documented in the subject's case record. The instructions for preparing and administering pembrolizumab will be provided in the Pharmacy Manual.

Subjects who are unable to comply with protocol requirements (i.e. attend study visits within protocol prescribed windows, complete study assessments, etc.) may be removed from the protocol by the Investigator.

7.1.2 Clinical Procedures/Assessments

7.1.2.1 Adverse Event (AE) Monitoring

The investigator or qualified designee will assess each subject to evaluate for potential new or worsening AEs as specified in the Trial Flow Charts and more frequently if clinically indicated. Adverse experiences will be graded and recorded throughout the study and during the follow-up period according to NCI CTCAE Version 4.0 (see Section 12). Toxicities will be characterized in terms of seriousness, causality, toxicity grading and action taken with regard to trial treatment.

All AEs of unknown etiology associated with pembrolizumab exposure should be evaluated to determine if it is possibly an event of clinical interest (ECI) of a potentially immunologic etiology (irAE). See Section 5.7.2 and the separate guidance document in the study appendices regarding the identification, evaluation and management of AEs of a potential immunological etiology.

Please refer to section 7.2 for detailed information regarding the assessment and recording of AEs.

7.1.2.2 Full Physical Exam

The investigator or qualified designee will perform a complete physical exam during the screening period and at other time points as documented in Section 6. Clinically significant abnormal findings should be recorded.

7.1.2.3 Directed Physical Exam

For cycles that do not require a full physical exam per Section 6, the investigator or qualified designee will perform a directed physical exam as clinically indicated prior to trial treatment administration.

7.1.2.4 Vital Signs

The investigator or qualified designee will take vital signs at screening, prior to the administration of each dose of trial treatment and at other time points as specified in Section 6. Vital signs should include temperature, pulse, respiratory rate, blood pressure, pulse oximetry, and weight. Height will be measured at screening only.

7.1.2.5 Eastern Cooperative Oncology Group (ECOG) Performance Scale

The investigator or qualified designee will assess ECOG status (see Section 12.1) at screening, prior to the administration of each dose of trial treatment and at all other time points as specified in Section 6.0.

The investigator must review baseline images to confirm the subject has measurable disease per RECIST 1.1.

A PET/CT done as part of clinical practice prior to screening can be used if it meets the above qualifications and is within the stated time frame.

7.1.2.6.2. Tumor Imaging at 3 Months Post Completion of Radiation

A PET/CT scan will be required for imaging at 3 months post completion of radiation. CT scan should be diagnostic, including CT neck with IV contrast, CT chest with IV contrast, and CT abdomen/pelvis with IV and oral contrast. PET imaging should be completed as discussed in 7.1.2.6.1 above. If MRI neck has been done at baseline and will be the primary modality to follow the patient's head and neck disease, then MRI neck should be done at 3 months as well. CT scan is encouraged over MRI.

7.1.2.6.3 Subsequent Tumor Imaging

Subsequent tumor imaging will be with CT neck with IV contrast. Chest imaging will be with CT chest with IV contrast or chest X-ray PA/lateral as determined by response and time in follow up as detailed in section 6.0. MRI of the neck may be done as the primary means of following the patients' disease if this is determined to be the most accurate study by the investigator. If MRI of the neck will be used, then the CT neck can be omitted. CT scans

are encouraged over MRI. Unless clinically indicated, the same imaging modality (MRI neck or CT neck) should be used throughout the study.

7.1.2.6.4 Assessment of Disease

7.1.2.6.4.1 Definitions

Measurable Lesions: Lesions that can be accurately measured in at least one dimension with longest diameter at least ≥ 10 mm on CT scan (or >20 mm by X-ray). Cystic lesions thought to represent cystic metastasis can be considered as measurable lesions.

Malignant Lymph Nodes: To be considered pathologically enlarged and measurable, a lymph node must be ≥ 15 mm when assessed by CT scan.

Non-measurable Lesions: All other lesions < 10 mm or lymph nodes < 15 mm by CT scan.

Target Lesions: All measurable lesions up to a maximum of 2 lesions per organ and up to 5 lesions in total, representative of all involved organs, should be identified as target lesions and recorded and measured at baseline. Target lesions should be selected on the basis of their size (lesions with the longest diameter), be representative of all involved organs, but in addition should be those that lend themselves to reproducible repeated measurements. It may be the case that, on occasion, the largest lesion does not lend itself to reproducible measurement. In this circumstance, the next largest lesion which can be measured reproducibly should be selected. A sum of the diameters (longest for non-nodal lesions, short axis for nodal lesions) for all target lesions will be calculated and reported as the baseline sum diameters. If lymph nodes are to be included in the sum, then only the short axis is added into the sum. The baseline sum diameters will be used as reference to further characterize any objective tumor regression in the measurable dimension of the disease.

Non-target Lesions: All other lesions (or sites of disease) including any measurable lesions over and above the 5 target lesions should be identified as non-target lesions and should also be recorded at baseline. Measurements of these lesions are not required, but the presence, absence, or in rare cases unequivocal progression of each should be noted throughout follow-up.

7.1.2.6.4.2 Evaluation of Disease Response

Response determination will be defined based on RECIST 1.1. (Table 8).

Table 8. Definition of Response in Target Lesions.

Response	Definition
Complete Response (CR)	Disappearance of all target lesions*
Partial Response (PR)	At least a 30% decrease in the sum of the diameters of target lesions, taking as reference the baseline sum diameters
Progressive Disease (PD)	At least a 20% increase in the sum of the diameters of target lesions compared to baseline sum of target lesions, or any new lesions
Stable Disease (SD)	Neither sufficient decrease to qualify as a PR or sufficient increase to qualify as PD

*After treatment of SCCHN patients with radiation it may be difficult to distinguish residual disease from treatment effect/normal tissue. This will be a critical consideration at 3 months post completion of radiation. As detailed above PET/CT can play a significant role in determination of residual disease at 3 months post completion of radiation. If a target lesion has decreased in size but has not completely resolved and the lesion is not PET avid (defined as an SUV that is not higher than background soft tissue) then the patient is considered to have a complete response. If a target lesion has decreased in size, but has not completely resolved, and it has any PET activity a biopsy can be done at the discretion of the investigator. If a biopsy done and is negative then the patient will be considered to have a complete response. If the biopsy shows residual malignancy or a biopsy is not done then the patient will be considered to have a partial response or stable disease as determined by RECIST 1.1.

Per RECIST 1.1, response should be confirmed by a repeat CT scan. The scan for confirmation of response may be performed at the earliest 4 weeks after imaging that showed response (if clinically indicated) or at the next scheduled scan.

Lesions that can be measured clinically on physical exam (skin lesions or palpable lymph nodes) will be measured by the investigator with the longest axis recorded. These measurements can be used to guide clinical decision making, for example prompting an earlier CT scan to evaluate disease. However, only measurements based on radiology will be used to determine response.

Table 9. Assessment of Non-Target Lesions

Response	Definition
Complete Response (CR)	Disappearance of all non-target lesions
Incomplete Response/Stable Disease (SD)	Persistence of one or more non-target lesions
Progressive Disease	Appearance of one or more new lesions and/or unequivocal progression of existing non-target lesions

Although a clear progression of “non-target” lesions only is exceptional, in such circumstances, the opinion of the treating physician should prevail.

7.1.2.6.4.3 Evaluation of Best Overall Response

The best overall response is the best response recorded from the start of the treatment until disease progression/recurrence.

Table 10. Best Overall Response

Target Lesions	Non-Target Lesions	New Lesions	Overall Response
CR	CR	No	CR
CR	PR/SD	No	PR
PR	Non-PD	No	PR
SD	Non-PD	No	SD
PD	Any	Yes or No	PD
Any	PD	Yes or No	PD
Any	Any	Yes	PD

Given the observed pattern of response with immunotherapy medications (anti-PD-1 mAb, anti- PD-L1 mAb, and Anti-CTLA4 mAb) where some patients develop evidence of progressive disease by RECIST 1.1, with significant increase in size of target lesions and/or new lesions, followed by regression of disease to SD or PR/CR², all imaging showing progressive disease by RECIST 1.1, in the absence of significant clinic deterioration of the patient will be confirmed with a repeat CT scan at least 4 weeks from the initial imaging showing progression. Clinically stable patients will continue treatment in the interim before this scan. If progressive disease is confirmed on subsequent imaging, the patient will be defined as having progressive disease and will be taken off of the study. Progressive disease by RECIST 1.1 with clinical deterioration by the patient will be counted as progressive disease, and study treatment will be discontinued.

Determination of clinical deterioration is at the discretion of the treating physician as defined by progression of disease at critical sites requiring urgent intervention (for example cord compression), or development of signs and symptoms of disease progression and/or significant decline in ECOG performance status.

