Patients that meet the eligibility criteria will undergo PET/CT for baseline imaging and will require tumor tissue for evaluation for PD-L1 expression. Fresh tissue or archival tissue will be obtained and used for PD-L1 analysis. PD-L1 expression will not be required for entry onto the study, given it is unknown if PD-L1 is predictive when pembrolizumab is combined with radiation, and given preclinical data suggesting that radiation leads to an increase in IFN- γ and subsequent PD-L1 expression in the tumor.¹ As highlighted in the study schema, patients will be treated with radiation (1.2Gy BID for total 60Gy) concurrent with pembrolizumab at 200mg intravenous every 3 weeks. The first dosage of pembrolizumab will be given on the first or second day of radiation. After completion of radiation treatment, patients will continue to receive pembrolizumab as a single agent for 3 months. At 3 months after completion of radiation, all patients will undergo a PET/CT to evaluate for response. Patients with a complete response (CR) at 3 months will discontinue pembrolizumab therapy and be observed with clinical exam and repeat CT neck at least every 3 months in the first year and every 6 months in year 2. These patients will then have continued annual follow-up with physical exam and CT neck (as clinically indicated) until the end of the study. Patients with a partial response or stable disease will continue treatment with pembrolizumab up to a total of 24 months (104 weeks) from the first cycle of treatment as long as they do not develop progressive disease, an intolerable toxicity, or other criteria for study withdrawal. These patients will be monitored with CT neck/chest after every 3rd cycle of pembrolizumab or more frequently if clinically indicated. Patients with progressive disease at 3 months post reirradiation will be taken off pembrolizumab and followed for survival. A patient who achieves a CR at 3 months post reirradiation and subsequently progresses may be eligible for retreatment with pembrolizumab as a single agent for up to one year. However, only the time to initial progression will be included in the PFS analysis, the primary endpoint of the study. Determination of response will be as per RECIST 1.1. However, given the experience with immune co-signaling blockade and the possibility of an inflammatory reaction leading to an increase in size of target lesions as well as the development of new lesions initially (before subsequent regression), progressive disease in the absence of clinical deterioration will be verified with repeat CT imaging not less than 4 weeks from prior imaging.^{2,3}

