8.2.3 Efficacy

Endpoints Primary

Progression-free survival (PFS) – Progression free survival is defined as the time from the initiation of treatment to the first documented disease progression per RECIST 1.1 or death due to any cause, whichever occurs first. If a patient recurs and is eligible for retreatment, then only the time to the initial recurrence will be included in the evaluation of PFS. Patients who are alive with no evidence of disease at the time of last contact will be censored at that date.

Secondary

Overall Response Rate (ORR) – The overall response rate is defined as the percentage of the patients who have a complete response (CR) or partial response (PR) as defined by RECIST 1.1. The patient's best overall response rate defined as the best response recorded from the start of the treatment until disease progression will be recorded.

Clinical Benefit Rate (CBR) - Clinical benefit rate is the percentage of patients that have achieved a complete response, partial response, and stable disease as defined by RECIST 1.1.

Time to in-field progression – The time to in-field progression is defined as the time from initiation of treatment to progression of disease within the radiation field.

Overall Survival – Overall survival is defined as the time from first treatment until death. Patients who are alive will be censored at the last date of patient contact.

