12.2 Common Terminology Criteria for Adverse Events V4.0 (CTCAE)

The descriptions and grading scales found in the revised NCI Common Terminology Criteria for Adverse Events (CTCAE) version 4.0 will be utilized for adverse event reporting. (<http://ctep.cancer.gov/reporting/ctc.html>).

12.3 Response Evaluation Criteria in Solid Tumors (RECIST) 1.1 Criteria for Evaluating Response in Solid Tumors

RECIST version 1.1* will be used in this study for assessment of tumor response. While either CT or MRI may be utilized, as per RECIST 1.1, CT is the preferred imaging technique in this study.

* As published in the European Journal of Cancer: E.A. Eisenhauer, P. Therasse, J. Bogaerts, L.H. Schwartz, D. Sargent, R. Ford, J. Dancey, S. Arbuck, S. Gwyther, M. Mooney, L. Rubinstein, L. Shankar, L. Dodd, R. Kaplan, D. Lacombe, J. Verweij. New response evaluation criteria in solid tumors: Revised RECIST guideline (version 1.1). Eur J Cancer. 2009 Jan;45(2):228-47.

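### Table 8 sets no minimum increase in millimetres for target-lesion progression and does not say whether it or RECIST 1.1 governs, so measurement noise can create PFS events when the target sum is small

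*Combined protocol and SAP*

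**What the plan says.** Section 7.1.2.6.4.2 introduces its response table with "Response determination will be defined based on RECIST 1.1. (Table 8". The progressive-disease row of that table reads "At least a 20% increase in the sum of the diameters of target lesions compared to baseline sum of target lesions", or any new lesion. No absolute minimum is printed there or elsewhere in the document.

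Three other parts of the plan bear on how this row is used.

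- **Entry and measurability.** A non-nodal lesion of 10 mm on CT is measurable, as is a node of 15 mm (section 7.1.2.6.4.1). One measurable area is enough for entry (section 5.1.2, criterion 9). A total target sum of 10-15 mm is therefore allowed.
- **The primary endpoint.** Section 8.2.3 counts "the first documented disease progression per RECIST 1.1 or death due to any cause, whichever occurs first". It does not cite Table 8 or mention confirmation. Section 12.3 adds that "RECIST version 1.1* will be used in this study for assessment of tumor response", without reproducing the criteria.
- **Confirmation.** Section 7.1.2.6.4.3 says that imaging progression without significant clinical deterioration "will be confirmed with a repeat CT scan at least 4 weeks from the initial imaging showing progression". It continues: "If progressive disease is confirmed on subsequent imaging, the patient will be defined as having progressive disease and will be taken off of the study". Section 2.1 has the same rule.

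**The concern.** A purely relative threshold shrinks with the lesion. At the smallest sums allowed, 20% is a difference that could come from reading error alone. Table 8 is the only numeric progression rule in the document, so a site reader or the programmer deriving PFS may apply it as printed. The references to RECIST 1.1 do not settle the matter, because the plan does not say which text prevails if they differ.

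At stake is the primary endpoint. A patient with an unchanged small lesion could be given a PFS event. That shortens recorded PFS and costs power, but it does not produce a false claim of benefit. The plan is also unclear on whether an unconfirmed reading counts: section 8.2.3 takes the first documented progression, while section 7.1.2.6.4.3 defines progression only once it is confirmed.

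**Working it through.** **1. The plan's power figure.** Inputs from section 8.2.2: 48 patients at 2 per month (24 months of accrual), 12 months of further follow-up, median PFS 8 versus 12 months, one-sided 5%. Assume exponential PFS and uniform accrual.

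- Hazards: ln 2/8 = 0.0866 and ln 2/12 = 0.0578 per month, ratio 1.50.
- Event probability under the 12-month median: 1 − (e^(−0.0578×12) − e^(−0.0578×36))/(0.0578×24) = 0.729. Expected events: 48 × 0.729 = 35.0.
- Power: Φ(√35 × ln 1.50 − 1.645) = Φ(0.754) = 77.5%. The stated 78% is reproduced.

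**2. What 20% means in millimetres.** It is 2.0 mm at a sum of 10, 3.0 at 15, 4.0 at 20 and 5.0 at 25. A 5 mm minimum would therefore matter only for sums below 5/0.20 = 25 mm.

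**3. False progression with no true change.** The documents give no reading error, so this is an assumption: independent normal error on each reading, SD 1.0 mm, with 0.75 and 1.5 as the range. Readings are rounded to 1 mm, the baseline reading must be at least 10 mm, and there are five follow-up scans (week 17, then after every third 3-week cycle, gives about five in the first year). Each scan has an independent confirming scan. There were 400,000 simulated patients per setting. Results at SD 1.0 mm:

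| True sum | At least one scan ≥ 20% | Confirming scan also ≥ 20% | At least one scan ≥ 20% and ≥ 5 mm |
|---|---|---|---|
| 10 mm | 16% | 1.2% | 0.0% |
| 12 mm | 14% | 6.4% | 0.2% |
| 15 mm | 14% | 3.5% | 0.4% |
| 20 mm | 3% | 0.4% | 0.4% |
| 25 mm | 0.4% | 0.0% | 0.4% |

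At 10-15 mm, across SDs of 0.75 to 1.5 mm, the first column runs from 4% to 33% and the second from 0.2% to 14%. The third is at most 7%. Confirmation does not remove the problem, because both scans are compared with the same baseline reading, which may itself have been too low.

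**4. Effect on power.** Assume that 30% of patients have sums of 10-15 mm and that half of those stay near baseline size, so 0.30 × 0.50 = 15% are exposed. The documents support neither share. With false-progression probability r over about 12 months, the added hazard is 0.15 × (−ln(1 − r))/12, and power is Φ(√35 × ln(0.0866/new hazard) − 1.645).

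| r | New hazard | Ratio | Power |
|---|---|---|---|
| 1.2% (confirmed, 10 mm) | 0.0579 | 1.496 | 77.0% |
| 3.5% (confirmed, 15 mm) | 0.0582 | 1.489 | 76.1% |
| 6.4% (confirmed, 12 mm) | 0.0586 | 1.479 | 74.8% |
| 14% (unconfirmed) | 0.0596 | 1.453 | 71% |

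**5. The opposite effect in the same row.** The reference is the baseline sum. A lesion that shrinks from 15 to 10 mm must reach 1.2 × 15 = 18 mm, 80% above its smallest size, before Table 8 calls progression.

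**The case against.** The strongest reply is that Table 8 is only a summary. The PFS event is defined by RECIST 1.1 and the appendix adopts that standard, so any minimum in the standard already applies. This has force: the printed row cannot be called the settled endpoint rule. It does not close the gap, because the plan reproduces no other numeric rule and gives no order of precedence. The point does not depend on what RECIST 1.1 contains, which the documents do not show.

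The second reply is the confirming CT, which section 2.1 also requires: "progressive disease in the absence of clinical deterioration will be verified with repeat CT imaging not less than 4 weeks from prior imaging". This stands and cuts the rate substantially. A reader might infer that power falls from 78% to 71%, but that figure uses the unconfirmed rate and applies only if section 8.2.3 is read as ignoring confirmation.

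Third, patients receive 60 Gy and many lesions should shrink. With 10% shrinkage at SD 1.0 mm, confirmed false progression over five scans falls to 0.01%, 1.6% and 0.1% at 10, 12 and 15 mm. A shrunken lesion without PET avidity at 3 months is classed as a complete response (Table 8 footnote), and imaging evidence of recurrence in that follow-up is biopsied (section 6.2). This also stands, and it limits the concern to lesions that stay near baseline size.

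A reader might also set 2-3 mm against the 0.3 cm slice limit in section 5.2.1.3. That limit is for the radiotherapy simulation CT and says nothing about reading error on response scans.

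**Conclusion.** The concern holds as a gap in the endpoint definition, of minor to moderate severity. Table 8 prints no absolute minimum, the plan does not say which text governs, and literal use lets 2-3 mm count as progression at target sums of 10-15 mm. False PFS events can follow. The effect is confined to sums below 25 mm in lesions near baseline size, and it biases against the treatment.

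In exposed patients the confirmed rate is 1-6% at an assumed SD of 1.0 mm. The resulting power loss, from about 78% to about 75-77%, also rests on the assumed 15% exposed share.

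It would be tempting to conclude that false events are being recorded in patients with stable disease, or that Table 8 as a whole brings progression forward. The documents support neither: they give no lesion sizes or reading error, and the baseline reference delays progression in lesions that shrink and regrow.

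**What to change.** For the PFS event in section 8.2.3:

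- Require both a 20% relative increase and an absolute minimum increase in the target sum, or any new lesion. The minimum is a choice that the documents do not supply; 5 mm works in the simulation. The non-target route in Table 9 can stay as it is.
- State that the confirmation rule of section 7.1.2.6.4.3 applies, and whether the first or the confirming scan dates the event.
- Reconcile Table 8 with the criteria named in section 12.3 by stating which governs where they differ.

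Because the trial is open-label with a single arm, fix the rule before the PFS analysis, apply it uniformly to all recorded diameters, and report PFS under the printed 20%-only rule as a sensitivity analysis.

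The cost is a few sentences and one added condition in the PFS derivation, with no new scans. The downside is that true growth of 2-4 mm in a very small lesion is called about one scan later. Table 8 progression also bears on stopping treatment (sections 5.9.1 and 7.1.2.6.4.3). This proposal covers only the PFS event; any effect on discontinuation is for the sponsor to reconcile.
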